3.5 Evaluation Schedule and Definitions

Patients will be followed from baseline until Day 180. Following Day 180, a second optional interventional period from Day 180 to Day 360 may be initiated per the joint decision of the patients with their study physician.

3.5.1 Baseline

The baseline visit marks the beginning of the interventional phase. Patients will receive training and onboarding with Abilify MyCite based on the commercial training materials for Abilify MyCite to reflect real-world practice. Baseline assessments include: demographic data, medical and psychiatric history, height, weight, and corresponding calculated body mass index (BMI), vital signs, and hospitalization history (all-cause and psychiatric). CCI

For analysis, baseline includes assessments conducted and patient data collected at or prior to the baseline visit and before first use of Abilify MyCite.

3.5.2 Interventional Period

The interventional period is from baseline to Day 180. Patients will use Abilify MyCite from baseline through Day 90. Day 91 through Day 180 is an Abilify MyCite nonuse period during which patients will continue with oral aripiprazole or other appropriate treatment, per routine clinical care.

After the baseline visit, there are no mandated visits until Day 180. However, it is anticipated that patients will undergo medical evaluation at regular intervals. Data collected at these routine care visits include Abilify MyCite use changes and adverse events (AEs). CCI

¹⁷ Garri do MM, Kel l ey AS, Pari s J, Roza K, Mei er DE, Morri son RS, Al dri dge MD. Methods for constructi ng assessi ng propensi ty scores. Heal th servi ces research. 2014 Oct 1; 49(5):1701

¹⁸ Austi n PC. Opti mal cal i per wi dths for propensi ty matchi ng wheresti mati ng di fferences i n means and di fferences i n proporti ons i n observati onal studi es. Pharm Stat 2010; 2(1):5061

CCI

3.5.3 Mid-Study (or End of Study) visit (Day 180)

The Day 180 (± 7) visit marks the end of the interventional phase. All patients will complete the Day 180 visit. Data collected at the Day 180 visit includes Abilify MyCite use changes and AEs.

CCI

At the Day 180 visit, a second, optional interventional period (up to 6 months of Abilify MyCite; Day 180 through up to Day 360) may be initiated per the joint decision of the patients with their study physician; if the patient is not continuing into the optional second interventional period (section 3.5.4), then the Day 180 visit is the final visit.

3.5.4 Optional Second Interventional Period

At the Day 180 visit (or later during the Day 180 through up to 360 period), patients will decide jointly with their study physician whether to restart Abilify MyCite for a second interventional period (Day 180 through up to 360). Patients will re-initiate Abilify MyCite and the second interventional period will proceed similarly to the interventional period (section 3.5.2). During this second, optional interventional period, patients may start and stop Abilify MyCite as clinically indicated.

Data collected at routine care visits between Day 180 and Day 360 will include Abilify MyCite use changes and AEs.

3.5.5 End of Study (Day 360)

The Day 360 visit marks the end of the second optional interventional phase. Data collected at the Day 360 visit includes Abilify MyCite use changes and AEs. CCI

3.5.6 Early Terminations

If a patient withdraws or is withdrawn from the study prematurely (e.g., before completing the scheduled Day 180 or Day 360 visit, if applicable), then an early termination (ET) visit should be performed, at which time all assessments and procedures that were to have been performed at the Day 180 or Day 360 (if applicable) visit should be completed. In such cases, the reason for the ET must be recorded.

4.0 STATISTICAL METHODOLOGY

4.1 General Considerations

Statistical analyses will be performed using SAS[®] version 9.4 or higher computer software.

Analyses will utilize prospectively collected clinical data from study sites, data collected from Abilify MyCite, CCI [REDACTED]

[REDACTED] Data from all sources will be integrated into one dataset for analysis.

Patient characteristics, treatments and outcomes will be tabulated and summarized with descriptive statistics. All descriptive summaries will include means, medians, standard deviation (SD) and ranges for continuous variables and absolute/relative frequencies for categorical data. Statistics will be summarized for the study population overall and by treatment arm.

Raw data (i.e., minimum and maximum values presented for range in continuous variables) will be reported out to the precision with which it was collected. Means will be reported to 1 decimal place more than the raw data. SD will be reported to 1 decimal place more than the mean. Percentages will be reported to 1 decimal place. Trailing zeros will be presented to maintain a consistent level of precision, e.g. 2.0 rather than 2.

Inferential tests will be performed at the 5% level of significance. All p-values will be rounded to 3 decimal places. If a rounded p-value is 0.000 (i.e., the actual p-value is less than 0.0005), then the p-value will be presented as '< 0.001.'

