3.3.4 Patient Inclusion Criteria

For enrollment into the study, patients are required to meet the following inclusion criteria:

Table 3.3.4-1 Inclusion Criteria	
1.	Patients are actively enrolled in an Anthem-affiliated commercial, Medicaid, or Medicare health plan with medical and pharmacy benefits.
2.	Male and female patients between the ages of 18 and 63 years, inclusive at the time of consent.
3.	Patients must have a smartphone with data plan.
4.	Patients must have a current diagnosis of SCH, BP1, or MDD.
5.	Patients currently prescribed aripiprazole, or appropriate for aripiprazole treatment.
6.	Within 60 days prior to study enrollment, patients are required to have had a hospitalization (all cause or psychiatric) or at least 1 psychiatric partial hospital admission.
7.	Patients are deemed appropriate, per the study physician judgment, to use Abilify MyCite per the package insert and to enter this interventional study.
8.	Patients must be able to read and understand English.

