5.1 Data Sources

Data sources for this study include demographic and clinical data collected prospectively by study sites, data collected from Abilify MyCite, CCI

CCI [REDACTED] In order to maintain patient confidentiality, each patient will be assigned a unique study-specific patient ID upon study enrollment to use in place of the patient name or any other identifying information (eg, medical record number). Data collected from Abilify MyCite will be transferred to HealthCore and integrated with prospectively collected study data, CCI [REDACTED] will be leveraged for analysis.

For data through the electronic case report forms (eCRFs), the study physician has the ultimate responsibility for the collection and reporting of all clinical and patient data and ensuring that the data are accurate and complete.

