7.1 Sample Size

The primary endpoint for the study is the proportion of patients with at least 1 all-cause hospitalization from study start date to Day 180. The assumptions for the sample size calculation were based on input from [REDACTED] for patients diagnosed with SCH, BP1, or MDD who had at least 1 all-cause hospitalization or partial psychiatric hospitalization within the 60 days prior to enrollment. A control group event rate of 36.3% was estimated, weighted based on an expected study distribution of 25% patients with SCH, 25% with BP1, and 50% with MDD. Sample size calculations were based on testing 2 proportions using the Z-test with unpooled variance. The study sample size of 447 patients was calculated based on the following assumptions, informed from [REDACTED] 20% reduction in the proportion of patients with all-cause hospitalizations in the Abilify MyCite group versus the virtual matched control group (29.04% Abilify MyCite versus 36.30% virtual matched control), 1:3 (Abilify MyCite : virtual matched controls) matching, 80% power, and maintaining an overall alpha level of 0.05 with the level of significance in a superiority hypothesis of 0.025. Sample size calculations will be documented in the SAP. Using a 30% dropout rate at 6 months, a sample size of 640 patients will need to be enrolled to ensure completion of 447 patients.

A virtual control group of approximately 1350 patients will be identified from the [REDACTED] and matched to the final sample of Abilify MyCite patients. This will create 3 controls for every 1 Abilify MyCite patient, which reduces the required Abilify MyCite sample size as compared to a 1:1 match while maintaining statistical power. Controls will be matched to Abilify MyCite patients using a propensity score derived from [REDACTED]. This process has been shown to minimize bias associated with sample selection. Further details on the matching process will be included in the SAP.

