- ≥ 180 days of medical and pharmacy enrollment following index date

Prior to matching, the pool of potential controls and the Abilify MyCite cohort will be stratified by psychiatric diagnosis (SCH, BP1, MDD). The Abilify MyCite cohort psychiatric diagnosis will be based on the psychiatric diagnosis recorded in the eCRF. The potential controls psychiatric diagnosis will be based on the psychiatric diagnosis identified [REDACTED] CCI. In the event that more than one of the qualifying psychiatric diagnoses is identified [REDACTED] CCI, the following hierarchy will be applied to potential controls: SCH>BP1>MDD.

From this pool of patients, combined with the active arm, logistic regression will be used within each psychiatric diagnosis to estimate a propensity score for each patient, where propensity refers to a patient's pre-index likelihood to be in the active arm. The dependent variable equals 1 for patients in the active arm and 0 for the controls. The following variables may be considered for inclusion in the propensity score model; a final determination will be made using descriptive study results on patient baseline characteristics.

- Age
- Gender
- Month of index date
- Plan type (commercial, Medicaid, or Medicare health plan with medical and pharmacy benefits)
- Number of fills for any atypical antipsychotic over 6-12 months prior to index date
- [REDACTED] CCI
- Occurrence/number of visits with a psychiatrist over 6-12 months prior to index date
- Comorbidities over 6-12 months prior to index date

¹⁶ Defined as a medical claim with place of service code = 52 ("Psychiatric Hospitalization"), or with HCPCS codes H0035 or S0201.

- Region of patient residence (Northeast, South, Midwest, West)

The estimated propensity scores will be used to match active arm patients to the virtual controls in a 1:3 ratio. Prior to assessing outcomes, the validity of the propensity score adjustment will be assessed by (1) graphically examining the overlap in propensity scores across treatment and control groups¹⁷, and (2) comparing balance in all baseline characteristics across the cohorts via standardized mean differences. A standardized mean difference >10% in absolute value will be used to indicate potential imbalance that may warrant further investigation or adjustment (e.g. through regression analysis).¹⁸ Propensity score models will be finalized prior to the assessment of outcomes.

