4.2 Sample Size Estimation

The primary endpoint for the study is the difference in the proportion of patients with at least 1 all-cause hospitalization for the Abilify MyCite versus virtual matched control cohorts from baseline to Day 180. The sample size calculation assumptions were based on input CCI [REDACTED] for patients diagnosed with SCH, BP1, or MDD who had at least 1 all-cause hospitalization or partial psychiatric hospitalization within the 60 days prior to enrollment. A control group event rate of 36.3% was estimated, weighted based on an expected study distribution of 25% patients with SCH, 25% with BP1, and 50% with MDD. Sample size calculations were based on testing 2 proportions using the Z-test with unpolled variance.

The study sample size of 447 patients was calculated based on the following assumptions, CCI [REDACTED]: 20% reduction in the proportion of patients with all-cause hospitalizations in the Abilify MyCite group versus the virtual matched control group (29.04% Abilify MyCite versus 36.30% virtual matched control), 1:3 (Abilify MyCite:virtual matched controls) matching, 80% power, and maintaining an overall alpha level of 0.05 with the level of significance in a superiority hypothesis of 0.025. Using a 30% dropout rate at 6 months, a sample size of 640 patients will need to be enrolled to ensure completion of 447 patients.

A virtual control group of approximately 1350 patients will be identified CCI [REDACTED] and matched to the final sample of Abilify MyCite patients. This will create 3 controls for every 1

Abilify MyCite patient, which reduces the required Abilify MyCite sample size as compared to a 1:1 match while maintaining statistical power. Controls will be matched to Abilify MyCite patients using a propensity score (please see section 3.4) [REDACTED]. If a sufficient population of controls is not identified to support matching in a 1:3 (Abilify MyCite:virtual matched controls) ratio, the matching ratio will be decreased sequentially to 1:2 followed by 1:1 if necessary.

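### The visible plan does not ensure that 180-day hospitalization is measured alike in both arms: plan coverage to Day 180 is required of controls, but only coverage at entry is required of MyCite patients.

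*SAP*

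**What the plan says.** **Coverage, controls.** SAP 3.4 lists among the conditions for the control pool "≥ 180 days of medical and pharmacy enrollment following index date". The same section expects some control attrition from lost insurance, but only for the 12-month analyses.

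**Coverage, MyCite arm.** The corresponding condition in Protocol 3.3.4 is "Patients are actively enrolled in an Anthem-affiliated commercial, Medicaid, or Medicare health plan with medical and pharmacy benefits". It is an entry criterion with no duration. SAP 5.1.2 defines the analysis population by eligibility and attendance at Day 180. Lost coverage is not among the withdrawal criteria listed in Protocol 3.6.3; section 3.6.4, which follows, is redacted.

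**Sources.** Protocol 5.1 begins "Data sources for this study include demographic and clinical data collected prospectively by study sites, data collected from Abilify MyCite" and then continues into redacted text. SAP 4.1 has a similar list, also partly redacted, followed by "Data from all sources will be integrated into one dataset for analysis". In Protocol Table 3.5.1-1, hospitalizations are marked only in a Days 1-360 column whose header is redacted. Footnote h says these data are gathered where routine care provides them and, after a redaction, refers to a three-month lag after study completion. Protocol 4.2 tells sites to take care in recording hospitalizations.

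**Endpoint.** Protocol 3.4.1 and 7.3.1 and SAP 4.4 define the primary endpoint as the proportion hospitalized by Day 180. None of them names the data source or says how a person without coverage is handled.

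**The concern.** The primary comparison is a difference between two proportions, so an event must have the same chance of being recorded in each arm. By construction, every control can be observed in the plan's data for the full 180 days. A MyCite patient can leave the plan on, say, Day 60, attend on Day 180 and remain in the analysis. If events are read from claims, an admission on Day 100 leaves no trace and the patient counts as not hospitalized. The missing-data rule in the SAP (no imputation, missing values excluded from percentages) does not catch this, because an unseen admission looks like a non-event and not like a missing value. The error runs in the direction of the trial hypothesis.

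A second uncertainty pulls the other way. Controls have no study site. If an admission known only to a site can count, the MyCite arm has a source that controls lack.

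**Working it through.** **Inputs**
- Rates "29.04% Abilify MyCite versus 36.30% virtual matched control" (SAP 4.2): difference 36.30 − 29.04 = 7.26 points.
- Three controls per MyCite patient, power of 80% and a one-sided significance level of 0.025 (SAP 4.2).
- Method: "testing 2 proportions using the Z-test with unpooled variance" (Protocol 7.1).
- Planned numbers: 447 MyCite completers, hence 3 × 447 = 1341 controls.
- Assumptions, not in the documents: the share L of analysed MyCite patients who lose coverage, loss at Day 90, constant hazard, no later admission seen.

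**Step 1. The plan's own figure.** n = (1.960 + 0.842)² × [p₁(1−p₁) + p₂(1−p₂)/3] / (p₁−p₂)², where p₁ belongs to the arm with one share.
- MyCite as the one-share arm: 7.849 × [0.2061 + 0.2312/3] / 0.00527 = 421.6, so 422.
- Rates swapped between arms: 7.849 × [0.2312 + 0.2061/3] / 0.00527 = 446.6, so 447.

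The printed 447 is reproduced exactly only with the rates swapped. That is a separate and slightly conservative slip. At 447 versus 1341, power with the rates as written is 82.2%. The calculation treats the groups as independent, whereas SAP 4.4 plans McNemar's test, so the error rates and powers below are approximate.

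**Step 2. Coverage loss with no true effect (36.3% in both arms).**
- Probability of an event by Day 90: 1 − √(1 − 0.363) = 0.2019.
- Probability of a first event after Day 90: 0.363 − 0.2019 = 0.1611.
- Fall in the observed MyCite rate: L × 0.1611.
- False-positive rate: Φ(d/SE − 1.960), where d is the fall and SE = √[p(1−p)/447 + 0.363 × 0.637/1341] at the observed MyCite rate p.

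| L | Fall (points) | Share of 7.26 | Observed MyCite rate | False-positive rate (nominal 2.5%) |
|---|---|---|---|---|
| 5% | 0.8 | 11% | 35.5% | 4.9% |
| 10% | 1.6 | 22% | 34.7% | 9.0% |
| 20% | 3.2 | 44% | 33.1% | 23.8% |

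Spreading the loss uniformly over the 180 days gives nearly the same false-positive rates: 5.1%, 9.4% and 25.5%.

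**Step 3. If site reports also count.** Two things change.
- Sites recover part of what lost coverage hides. If they hear of 30% to 70% of those admissions (an assumption), the 1.6-point fall at L = 10% shrinks to 1.6 × 0.7 = 1.1 or 1.6 × 0.3 = 0.5 points.
- Sites may add events that claims would miss in either arm. If this raised the recorded MyCite rate by a relative 5% under the planned rates (29.04% × 1.05 = 30.5%), power would drop from 82.2% to 62.7%.

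Step 2 assumes that sites contribute nothing, so its figures cannot be combined at full size with an over-capture effect that assumes they contribute much.

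**The case against.** A reader might infer from "Data from all sources will be integrated into one dataset for analysis" that the MyCite arm's primary events are drawn from more sources than the controls', and that the outcome is therefore a different measurement in each arm. The documents do not support that. The sentence is general data handling, follows a partly redacted source list and sets no event rule. Visible clues point towards a single administrative extract: hospitalizations are scheduled in the redacted-header column and not at site visits, and a three-month lag suits claims better than site entry. The matching footnote g in the exploratory study omits the routine-practice condition. Footnote 16 of SAP 3.4 is no evidence about outcomes either; it codes partial psychiatric hospitalization as a qualifying event before index. That control outcomes come from claims is a fair inference, not a stated rule.

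It can also be said that redacted Protocol 3.6.4 might deal with lost coverage, that some patients who lose coverage will miss Day 180 and leave the analysis set, and that the loss rates used here are invented. These points limit what can be claimed about size. They do not remove the visible mismatch between an entry-only condition and a 180-day condition. If events are counted from claims in both arms, as the clues suggest, the source question disappears and the coverage bias remains in full.

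The study stopped after two patients with no efficacy assessment (SAP 5.0), so this concerns the plan and not a result.

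**Conclusion.** The concern holds in a limited form: the unredacted text does not ensure equal measurement of the primary outcome. The coverage mismatch is explicit. With claims-based events it biases towards MyCite, by about 0.8 to 3.2 points if 5% to 20% of analysed MyCite patients lose coverage at Day 90, or 11% to 44% of the target difference. These sizes depend on the assumed loss rates, a constant hazard and no recovery of later events. Whether sites supply additional MyCite events is open; if they do, the coverage effect is smaller and an opposing one appears. The net bias is therefore unknown if both sources count. The documents do not support the stronger conclusion that the two arms are certainly measured differently.

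**What to change.** In SAP 4.4, define the primary endpoint in both arms from the same health-plan claims source, with one coded definition of an inpatient admission. Then apply one coverage rule to both arms:

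- **Simple option.** Require 180 days of post-index coverage in the MyCite primary analysis set as well, applied before matching. McNemar's test can stay; how it handles three controls per patient is a separate matter.
- **Alternative.** Drop the post-index enrollment condition for controls and censor both arms at disenrolment, with a test and variance suited to matched, censored data. Censoring while keeping that condition would act on the MyCite arm alone, and McNemar's test could not be used.

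Use site-reported hospitalizations only in a sensitivity analysis, and report how many have no matching claim.

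**Cost.** The simple option needs SAP wording and programming, with no new site data. The alternative changes the primary analysis. Some MyCite patients or genuine site-reported admissions leave the primary count. Under the simple option, if 10% of completers lost coverage, keeping 447 would take 447/0.9 = 497 completers. Either rule assumes that leaving the plan is unrelated to hospitalization risk, and the SAP should say so.

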4.2 Sample Size Estimation

The primary endpoint for the study is the difference in the proportion of patients with at least 1 all-cause hospitalization for the Abilify MyCite versus virtual matched control cohorts from baseline to Day 180. The sample size calculation assumptions were based on input CCI [REDACTED] for patients diagnosed with SCH, BP1, or MDD who had at least 1 all-cause hospitalization or partial psychiatric hospitalization within the 60 days prior to enrollment. A control group event rate of 36.3% was estimated, weighted based on an expected study distribution of 25% patients with SCH, 25% with BP1, and 50% with MDD. Sample size calculations were based on testing 2 proportions using the Z-test with unpolled variance.

The study sample size of 447 patients was calculated based on the following assumptions, CCI [REDACTED]: 20% reduction in the proportion of patients with all-cause hospitalizations in the Abilify MyCite group versus the virtual matched control group (29.04% Abilify MyCite versus 36.30% virtual matched control), 1:3 (Abilify MyCite:virtual matched controls) matching, 80% power, and maintaining an overall alpha level of 0.05 with the level of significance in a superiority hypothesis of 0.025. Using a 30% dropout rate at 6 months, a sample size of 640 patients will need to be enrolled to ensure completion of 447 patients.

A virtual control group of approximately 1350 patients will be identified CCI [REDACTED] and matched to the final sample of Abilify MyCite patients. This will create 3 controls for every 1

Abilify MyCite patient, which reduces the required Abilify MyCite sample size as compared to a 1:1 match while maintaining statistical power. Controls will be matched to Abilify MyCite patients using a propensity score (please see section 3.4) [REDACTED]. If a sufficient population of controls is not identified to support matching in a 1:3 (Abilify MyCite:virtual matched controls) ratio, the matching ratio will be decreased sequentially to 1:2 followed by 1:1 if necessary.

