4.4 Primary Endpoint

The primary endpoint is the difference in the proportion of patients with at least 1 all-cause hospitalization for the Abilify MyCite versus virtual matched control cohorts from baseline to Day 180. The primary endpoint analysis will be a McNemar's paired sample chi-square test between the treatment cohorts.

This test is directional in nature as it is testing the alternative hypothesis (H_A) that the proportion patients hospitalized will be lower in the Abilify MyCite cohort than the virtual control cohort. Adjustments will be made to the alpha level to account for the one-tail nature of the alternative hypothesis.

- $H_0: P_1 - P_2 \geq 0$ versus $H_A: P_1 - P_2 < 0$

Where:

- P_1 = proportion of Abilify MyCite patients with all-cause hospitalization from baseline to Day 180
- P_2 = proportion of virtual control patients with all-cause hospitalization from baseline to Day 180

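### The step-down from 1:3 to 1:2 or 1:1 matching has no stated scope or power and, read as one ratio for the cohort, discards matched controls in a partial shortage

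*SAP*

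**What the plan says.** SAP 4.2 ties the sample size to one design: "1:3 (Abilify MyCite:virtual matched controls) matching, 80% power", with assumed hospitalization proportions of "29.04% Abilify MyCite versus 36.30% virtual matched control". It credits the three controls per patient with a gain, "which reduces the required Abilify MyCite sample size as compared to a 1:1 match while maintaining statistical power". If not enough controls can be found for 1:3, "the matching ratio will be decreased sequentially to 1:2 followed by 1:1 if necessary".

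Neither SAP 4.2 nor Protocol 7.1 gives power or sample size for 1:2 or 1:1. Protocol 7.1 has no fallback and refers to the SAP for matching details.

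Three other SAP provisions bear on the point:
- **SAP 3.4, matching.** Matching is by propensity score within schizophrenia, bipolar 1 disorder and major depressive disorder. It is done after six-month (or early termination) data are in for all Abilify MyCite patients.
- **SAP 3.4, footnote 13.** The period from which controls are drawn may be extended if more are needed.
- **SAP 4.4.** The primary test is McNemar's paired chi-square test.

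**The concern.** The fallback names one ratio that moves as a unit. On that reading, if some Abilify MyCite patients can be given three acceptable controls and others only two, everyone goes to two and the third matches are dropped. If a few patients have only one, everyone goes to one. Information already in hand is lost in the very situation where controls are scarce.

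The scope is also open. Because matching is within diagnosis, a shortage in one diagnosis could lower the ratio for all three or only for that stratum, and the visible text does not settle which.

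The timing adds weight. The ratio is settled after the Abilify MyCite arm has been followed up, so further enrolment cannot recover lost power. A reader of the SAP cannot see how much power remains at 1:2 or 1:1.

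**Working it through.** **Inputs (SAP 4.2 unless noted)**
- p1 = 0.2904, p2 = 0.3630, so d = 0.0726 and d² = 0.00527076.
- p1(1 − p1) = 0.206068; p2(1 − p2) = 0.231231.
- Test for sizing: "Sample size calculations were based on testing 2 proportions using the Z-test with unpolled variance" (unpooled variance; Protocol 7.1 has the same test).
- Level: "maintaining an overall alpha level of 0.05 with the level of significance in a superiority hypothesis of 0.025", with SAP 4.4 adding "Adjustments will be made to the alpha level to account for the one-tail nature of the alternative hypothesis". Taken as one-sided 0.025, z = 1.960; for 80% power z = 0.842; (1.960 + 0.842)² = 7.849.
- Patients: "The study sample size of 447 patients was calculated based on the following assumptions".

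**Step 1. Reproduce 447.** With k controls per patient,

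n = [p1(1 − p1) + p2(1 − p2)/k] × 7.849 / d².

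At k = 3 this gives (0.206068 + 0.077077) × 7.849 / 0.00527076 = 421.6, so 422. Dividing the Abilify MyCite term by 3 instead gives (0.231231 + 0.068689) × 7.849 / 0.00527076 = 446.6, so 447 exactly. The pooled formula gives 441. The stated figure is therefore reproduced, and on the stated formula with three controls per patient it is slightly conservative. The dropout step also holds: 447/0.7 = 638.6, so 639 against the stated 640.

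**Step 2. Power at each fixed ratio, n = 447.**

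Power = Φ( d / √{[p1(1 − p1) + p2(1 − p2)/k]/447} − 1.960 ).

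| Ratio | Unpooled | Pooled | Weighting that returns 447 | Completers for 80% (unpooled) | Enrolled at 30% dropout |
|---|---|---|---|---|---|
| 1:3 | 82.2% | 80.6% | 80.0% | 422 | |
| 1:2 | 77.2% | 75.9% | 75.6% | 480 | 686 |
| 1:1 | 64.1% | 63.9% | 64.1% | 652 | 932 |

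The three variants agree within 2 points at 1:2 and 1:1. On the formula that gives 77.2% and 64.1%, the starting point is 82.2%, not 80%.

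**Step 3. Separate the rule from the shortage.** Keep every matched control, giving each of a patient's k controls weight 1/k. The control variance becomes p2(1 − p2) × v/447, where v is the average of 1/k over patients. The documents give no distribution of available controls, so the shares below are assumptions, shown as a range. The rest of the patients have three controls.

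| Assumed shortage | v | Matched controls | Kept at fixed ratio | Power, all kept | Power, fixed ratio | Gap (points) |
|---|---|---|---|---|---|---|
| 10% have two | 0.350 | 1,296 | 894 (1:2) | 81.7% | 77.2% | 4.5 |
| 50% have two | 0.417 | 1,118 | 894 (1:2) | 79.7% | 77.2% | 2.5 |
| 10% have one | 0.400 | 1,252 | 447 (1:1) | 80.2% | 64.1% | 16.1 |
| 50% have one | 0.667 | 894 | 447 (1:1) | 72.5% | 64.1% | 8.4 |

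Example, first row: v = 0.9/3 + 0.1/2 = 0.35, and matched controls = 447 × (0.9 × 3 + 0.1 × 2) = 1,296.

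**Step 4. A pool that is short overall.** Suppose 1,200 controls can be matched against the 1,341 needed (447 × 3). Then 306 patients have three and 141 have two, because 306 × 3 + 141 × 2 = 1,200, and v = (306/3 + 141/2)/447 = 0.386. Keeping all gives 80.6%. Fixed 1:2 uses 894, drops 306 and gives 77.2%.

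**Step 5. The SAP's primary test.** For McNemar on 447 pairs, with discordant proportion D,

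Power = Φ( [d√447 − 1.960√D] / √(D − d²) ).

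The within-pair correlation is not stated. Assumed values give:

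| Correlation | D | Power at 1:1 |
|---|---|---|
| 0 | 0.443 | 63.7% |
| 0.1 | 0.399 | 68.2% |
| 0.3 | 0.312 | 78.7% |

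**The case against.** The trigger can be read as a shortage of the pool, not of a few patients. If every patient has only two acceptable controls, 1:2 discards nothing and no matching scheme repairs the loss. That stands for a uniform shortage. It does not stand for a pool that is short but not evenly so, as Step 4 shows.

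The plan has safeguards ahead of the fallback. The control window can be extended, and potential controls with several qualifying episodes get an iterative search for the best match. Both make the fallback less likely. But the extension is optional, and the SAP sets no order between it and the step-down. The documents give no evidence either way on how likely a shortage is.

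Some of the matching text is redacted (in SAP 3.4 and 4.2, and in Protocol 3.5.4), so a finer rule may exist there. The point is limited to what can be read.

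Three stronger readings are tempting and are not supported:
- **That the fallback breaks the plan's stated 80% power.** The SAP attaches 80% to 1:3 only and itself says that a 1:1 match needs more Abilify MyCite patients. What is missing is the power at the lower ratios.
- **That the rule causes the whole fall to 77% or 64%.** Part of the fall comes from the shortage. Only the last column of the Step 3 table belongs to the rule, and it depends on assumed shares. With half the patients at one control, keeping everything still gives only 72.5%.
- **That 64% is the power of the planned 1:1 analysis.** It is the power of the sizing test, close to McNemar at zero correlation. With positive correlation McNemar does better.

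A pre-specified fixed-ratio fallback is a legitimate choice. The point is that a standard alternative keeps more information.

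**Conclusion.** The point holds as a modest improvement to the plan. The step-down has no stated scope and no restated power, and as a single ratio for the cohort it discards matched controls whenever the shortage is partial.

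In the scenarios worked, the cost of the rule itself is 2.5 to 4.5 points of power when the short patients have two controls and 8.4 to 16.1 points when they have one. These figures rest on the SAP's event rates, 447 analysed patients, one-sided 0.025, independent observations and the assumed shares. At 1:1 under McNemar, power runs from about 64% to 79% for assumed correlations of 0 to 0.3, below 80% throughout.

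There is no consequence for results. SAP 5.0 records that the study ended after two subjects with no efficacy assessment, so the matching rule matters only as a matter of planning.

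**What to change.** In SAP 3.4 and 4.2, replace the step-down with this sequence:
1. Apply any extension of the control window under footnote 13 before the ratio is settled, and say so.
2. Match up to three controls per Abilify MyCite patient within diagnosis, keeping however many acceptable matches each patient has.
3. Weight each control 1/k within its set, and report the distribution of k, and any patients with no match, before outcomes are examined.
4. In SAP 4.4, replace standard McNemar with an analysis that respects the sets and weights. One option is to average, over sets, the patient's outcome minus the mean outcome of that patient's controls, and to test that average one-sided at 0.025 with a variance taken across sets.
5. State the power at 1:3, 1:2 and 1:1. If a fixed-ratio fallback is kept, say whether it applies to the cohort or by diagnosis.

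The cost is a change to the SAP text that includes the primary test, and a slightly more complex weighted analysis. Standard McNemar handles 1:1 pairs only, so a matched-set analysis is already needed for the planned 1:3 design. The added burden is therefore small.
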